7.6.6 Vital Signs

Vital Signs will not be summarized.

8 CONVENTIONS

8.1 Age Definition

Age (years) will be calculated as:

$\frac{date \ of \ informed \ consent - date \ of \ birth + 1}{365.25}$

8.2 Duration and Study Day Definition

In instances in which study period between two dates are to be calculated (for example, duration of response, PFS and OS), the convention to be used is as follows: later date - earlier date + 1 day.

Study day is calculated as assessment date - first dose date + 1 day, if the assessment is taken on or after the first dose day. If the assessment is taken prior to the first dose day, study day will be calculated as assessment date - first dose date. Date of first dose is defined as Study Day 1.

8.3 Day Conversion of Date Imputation

Conversion from days to months or years:

- 1 year = 365.25 days
- 1 month = 30.4375 days

Imputation for partial or missing progression dates:

- If only the day is missing, the 1st of the month will be used to replace the missing day.
- If the day and month are missing or a date is completely missing, the date of progression will be moved back to the last complete tumor assessment date.

In both the cases given above, the imputed date will still be considered an event.

Imputation for partial or missing death dates:

- If only the day is missing, the later of the last known alive date and the 1st of the month will be used to replace the missing day.
- If both the day and the month are missing, the later of the last known alive date and Jan 1st will be used to replace the missing information.

In both the cases given above, the imputed date will still be considered an event.

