4.1.3 Primary Definition of Progression-Free Survival

Progression Free Survival (PFS) is defined as the time from first dosing date to the date of the first documented progression per IMWG uniform criteria or death due to any cause, whichever occurs first. Subjects who die without a reported prior progression will be considered to have progressed on the date of their death. Subjects who did not progress or die will be censored on the date of their last adequate tumor assessment. Subjects who did not have any on study efficacy assessments and did not die will be censored on the first dosing date.

Subjects who switched to subsequent therapy prior to documented progression will be censored on the date of the last adequate tumor assessment prior to the initiation of the new therapy.

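### SAP 8.3 dates a progression with a missing day to the 1st of the month with no floor, so a PFS event can precede a progression-free assessment or first dose

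*SAP*

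**What the plan says.** SAP 8.3 has two rules for incomplete progression dates.

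- Day missing: "If only the day is missing, the 1st of the month will be used to replace the missing day".
- Day and month missing, or no date at all: "the date of progression will be moved back to the last complete tumor assessment date".

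It then adds: "In both the cases given above, the imputed date will still be considered an event".

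The two death-date rules in the same section are built differently. With the day missing, "the later of the last known alive date and the 1st of the month will be used to replace the missing day". With day and month missing, "the later of the last known alive date and Jan 1st will be used to replace the missing information".

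SAP 4.1.3 measures PFS from first dose; it is "defined as the time from first dosing date to the date of the first documented progression per IMWG uniform criteria", or death if that comes first. For durations, including PFS, SAP 8.2 says "the convention to be used is as follows: later date - earlier date + 1 day".

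No lower limit for an imputed progression date appears in SAP 4.1.1 to 4.1.4, 7.5.1 or 8.2. SAP 8.4 refers partial dates to a sponsor convention, but for safety data only. Protocol 8.3.1.1 defines PFS without an imputation rule.

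**The concern.** The death rules cannot place a death before a date on which the subject was known to be alive. The day-missing progression rule has no matching protection against a date on which the subject was assessed as progression-free, or against the start of the PFS clock. An early date can be a defensible conservative choice. A date that contradicts a recorded negative assessment cannot, because the trial's own data show it to be wrong.

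The affected variable is the primary endpoint of the EPd cohort and a secondary endpoint of the EN cohort, under both PFS definitions in the SAP. If such a record arises, the programmer must either follow the rule into an impossible date or improvise a correction after the data have been seen, in an open-label trial.

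**Working it through.** The plan states no figure for this rule, so there is nothing to reproduce. The check applies the rule to the calendar.

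**Inputs.** Imputation and death-date rules: SAP 8.3. PFS origin: SAP 4.1.3. Duration formula: SAP 8.2. Assessments every 28 days from first dose: SAP 6.1; Protocol 4.5.8 keeps the cycles anchored to Cycle 1 Day 1. Calendar: four years, 1,461 days, 48 months. Assumption: true progression dates are spread evenly over the calendar, with no visit windows.

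**Condition.** Let *d* be the day of the month of the true progression and *g* the days since the last negative assessment. The rule moves the event back *d* − 1 days. The imputed date is before the negative assessment when *d* − 1 > *g*, by *d* − 1 − *g* days, and equal to it when *d* − 1 = *g*.

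**Progression at a scheduled visit (*g* = 28).**
- Before the negative visit: *d* = 30 or 31. Four years hold 44 + 28 = 72 such dates; 72/1,461 = 4.9%. The excess is 1 day (the 30th) or 2 days (the 31st).
- Same day as the negative visit: *d* = 29. There are 45 such dates; 45/1,461 = 3.1%.

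**Progression found off schedule.**

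| Days since negative assessment | Dates with imputed date strictly before it | Share |
|---|---|---|
| 7 | 1,461 − 8 × 48 = 1,077 | 74% |
| 14 | 1,461 − 15 × 48 = 741 | 51% |
| 21 | 1,461 − 22 × 48 = 405 | 28% |

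If the gap is assumed uniform over 1 to 28 days, the share is 49%, and the excess reaches 31 − 1 − 1 = 29 days.

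**Before first dose.** The same condition applies with first dose in place of the negative assessment. For progression at Cycle 2 Day 1 it is met when first dose falls on the 2nd of any month except February, or on the 3rd of a 31-day month: (44 + 28)/1,461 = 4.9% of start dates. For progression 7, 14 or 21 days after first dose the shares are again 74%, 51% and 28%.

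**What SAP 8.2 then returns.**
- First dose 2 May 2018, progression 30 May with the day missing. Imputed date 1 May, one day before first dose. Later minus earlier plus 1 = 2 − 1 + 1 = 2 days; the true value is 30 − 2 + 1 = 29 days.
- First dose 14 May, progression 28 May with the day missing. Imputed date 1 May, 13 days before first dose. The formula gives 14 − 1 + 1 = 14 days; the true value is 15. The result looks plausible although the event precedes treatment.

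**Size of the shift.** Over all 1,461 dates the mean of *d* − 1 is 14.7 days and the maximum is 30. The assumed EPd median of 15 months is 15 × 30.4375 = 457 days.

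**With a floor.** Negative visit 10 October, true progression 25 October, day missing: the present rule gives 1 October, 9 days before the negative visit; with the floor it is 11 October. In the 14 May example the date can be no earlier than 14 May.

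**The case against.** The strongest reply is that this is a conservative rule for a rare event. Serum and urine tests run every 4 weeks through the central laboratory (Protocol 5.4.1), and SAP 4.1.2 records that investigators were told to report the earliest measurement date of the time point as the progression date. Most progressions should therefore carry a full date. Early dating shortens PFS in a cohort hoped to reach 15 months against 11, so it cannot flatter the treatment. All of this stands, and it limits the size of the point. It does not justify a date that contradicts a recorded assessment. Partial dates also remain possible: marrow and imaging are done when clinically indicated, and local testing is allowed when a subject cannot attend.

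Four stronger readings are tempting, and the documents do not support them.

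- *Both progression rules lack a limit.* The rule for a missing month or date is anchored to an assessment. Its weakness is narrower: it relies on a 'complete' assessment, while SAP 4.1.1 defines an 'adequate' one. If no complete post-baseline assessment exists, the anchor could be the screening one, before first dose.
- *PFS could be zero or negative.* The SAP 8.2 duration formula subtracts the earlier date from the later and adds 1, so its minimum is 1. The error is a falsely positive value.
- *About 8% of day-missing progressions at scheduled visits would be dated before a negative visit.* The 8.0% (117/1,461) includes same-day ties; strictly before is 4.9%.
- *Dating an event at the last assessment when the month is missing is wrong, and a midpoint is needed.* Keeping the event at that date is a conservative choice. A midpoint is a preference, and the SAP's own death rules do not use one.

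**Conclusion.** The point holds, as a minor one. The day-missing progression rule in SAP 8.3 lacks the floor that the same section gives to deaths. As written, it can place a PFS event before a progression-free assessment or before first dose.

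The scheduled-visit figures (4.9% before, 3.1% tied) rest on an exact 28-day grid and evenly spread dates. The off-schedule shares rest on assumed gaps. All of them are conditional on the day being missing, and the documents give no rate for that. The number of affected subjects is unknown and probably small. Each affected event moves by at most 30 days, about 15 on average, and always earlier, so the effect on the median should be small. No sample size or power figure depends on the rule. This is a rule that can give a wrong date and is easily repaired; it does not threaten the primary result.

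**What to change.** In SAP 8.3, day-missing progression: use the latest of (a) the 1st of the month, (b) the day after the last adequate assessment without progression, and (c) the first dose date. Keep the record as an event.

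In the rule for a missing month or full date: replace 'complete' with 'adequate' as defined in SAP 4.1.1, and state that the imputed date is never before first dose. The rule otherwise stays as it is.

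The cost is one clause in each of two bullets and a small programming change. No new data are needed and no event is lost. The change should be made before any PFS dates are imputed for analysis.

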8.4 AE, Laboratory Results and Concomitant Medication

Safety data will be handled according to the BMS safety data conventions (described in "Analysis of Safety Data - Reference to CT SOP 109"). This document includes descriptions on how to analyze AE data as well as how to handle partial dates, missing dates, and unknown end dates when analyzing safety data.

The following dictionaries will be used to code medical terms and to derive toxicity grades:

- Adverse events and other symptoms will be graded according to the NCI CTC Version 3.0 and categorized according to the latest version of MedDRA at the time of analysis.
- Laboratory results will be classified according to the CTC Version 3.0 grading system.
- All medications will be coded as per the latest version of the WHO Drug dictionary at the time of analysis.
- Tables and listings for laboratory results will be available in SI units and US units.

9 CONTENT OF REPORTS

Statistical components for the clinical study report will be based on the content of this statistical analysis plan (SAP). It is assumed that a full CSR will be expected for the study CA204-142 at the writing of the SAP. If it is not the case, the SAP won't be updated. Details of the tables, listings, and figures to be prepared for the CSR will be included in a study-specific Data Presentation Plan (DPP).

9.1 Topline Analyses

Study conduct:

• Relevant eligibility deviations (Table and Listing)

Subject population:

- End of Treatment Summary
- Demographic Characteristics Summary
- Response to Most Recent Line of Therapy Summary
- Time from Diagnosis to First Dose Date

Extent of exposure:

• Number of Cycles Summary

Tumor response:

Best Overall Response

Progression free survival:

- Currentness of Follow-Up for PFS (Inv) Summary
- Kaplan-Meier plot of PFS Primary) (Figure)
- Kaplan-Meier plot of PFS (Secondary) (Figure)

Overall survival :

- Currentness of Follow-Up for Overall Survival Summary
- Kaplan-Meier plot of overall survival (Figure)

Safety:

- Adverse Event Summary by CTC Grade Combined
- Serious Adverse Event Summary by CTC Grade Combined
- Adverse Event Leading to Discontinuation Summary by CTC Grade Combined
- Infusion Reaction Summary by Common Terminology Criteria
- Deaths
- Deaths within 60 days of last study drug
- On study Hematology Lab Results
- On study Chemistry Lab Results

Specific tables corresponding to these topics will be identified in a separate Data Presentation Plan.

Table 4:	Document Histo	bry
Version Number	Author(s)	Description
0.1		Original version
0.2		Upated upon BMS comments on draft 1
0.3		Upated upon BMS comments on draft 2
0.4		Upated upon BMS comments
0.5		Updated upon protocol amendment 01
0.6		Updated upon protocol amendment 01 & BMS comments
1.0		Updated upon protocol amendment 01 & approved
1.1		
1.2		Updated upon protocol amendment 02 & BMS comments that include updates on draft amendment 03. There fore the SAP may not be consistent with the protocol whilst the amendment 03 is being finalized.
2.0		Updated upon draft of protocol amendment 03 received on 12Feb2018.
2.1		Added protocol amend 03 into section 2.4.
		Changed "last evaluable assessment" to "last adequate tumor assessment"
		Added sample size section 5.2 for EN cohort per amend 03

10 DOCUMENT HISTORY

	draft.
2.2	Updated the definition of response to most recent prior therapy.
	Updated the relevant protocol amendment.
	Updated the calculation of Elo omission.
2.3	Added Nivolumab dose intensity, relative dose intensity.
	Added derived reduction for Pomalidomide.

APPENDIX 1 LIST OF ABBREVIATIONS

Table 5:

List of Abbreviations

AE	Adverse Event
ATC	Anatomical Therapeutic Chemical
BMS	Bristol Myers Squibb
CI(s)	Confidence Interval(s)
CR	Complete Response
CRF	Case Report Form
CTCAE	Common Terminology Criteria for Adverse Events
DMC	Data Monitoring Committee
ECOG	Eastern Cooperative Oncology Group
EORTC	European Organization for Research and Treatment of Cancer
ESRD	End Stage Renal Disease
HRQOL	Health Related Quality of Life
ITT	Intent-to-Treat
IV	Intravenous
IVRS	Interactive Voice Response System
Ld	Pomalidomide, (low-dose) Dexamethasone
E-Ld	Elotuzumab, Pomalidomide, (low-dose) Dexamethasone,
MedDRA	Medical Dictionary for Regulatory Activities
MM	Multiple Myeloma
MR	Minor Response
ORR	Objective Response Rate
OS	Overall Survival
PD	Progression
DEC	

Table 5:	List of Abbreviations
РК	Pharmacokinetic
РО	Oral
PR	Partial Response
SAE	Serious Adverse Event
SAP	Statistical Analysis Plan
sCR	Stringent Complete Response
SD	Stable Disease
SE	Standard Error
SI	International System of Units (SI)
SOC	System Organ Class
STD	Standard Deviation
UD	Unable to Determine
ULN	Upper Limit of Normal
VGPR	Very Good Partial Response
WHO	World Health Organization

LIST OF MEDDRA TERMS TO BE INCLUDED AS INFUSION **APPENDIX 2 REACTIONS (PERI-INFUSIONAL ADVERSE EVENTS)**

Infusion reaction is a known Elotuzumab toxicity and a composite term "peri-infusional adverse event" will be created. This composite term is defined as any of the following, and will be updated at the time of the analysis, using the latest version of MedDRA.

MedDRA terms with a start date on the day of or the day after an infusion:

Table 6: **MedDRA** Terms ACUTE RESPIRATORY FAILURE ALLERGIC COUGH ALLERGIC OEDEMA ALLERGIC RESPIRATORY SYMPTOM ANAPHYLACTIC REACTION ANAPHYLACTIC SHOCK ANAPHYLACTOID REACTION ANAPHYLACTOID SHOCK ANGIOEDEMA APNOEA BLOOD PRESSURE DECREASED

Table 6:	MedDRA Terms	
BLOOD PRESSURE DI	ASTOLIC DECREASED	
BLOOD PRESSURE IM	IMEASURABLE	
BLOOD PRESSURE SYSTOLIC DECREASED		
BRADYCARDIA		
BRONCHIAL OEDEMA		
BRONCHOSPASM		
CARDIAC ARREST		
CARDIAC FAILURE A	CUTE	
CARDIO-RESPIRATORY ARREST		
CARDIO-RESPIRATORY DISTRESS		
CARDIOVASCULAR INSUFFICIENCY		
CHEST DISCOMFORT		
CHILLS		
CHOKING SENSATION		
CIRCULATORY COLL	APSE	
CIRCUMORAL OEDEN	ЛА	
COUGH		
DIASTOLIC HYPOTEN	ISION	
DIZZINESS		
DRUG HYPERSENSITI	IVITY	
DYSPHONIA		
DYSPNOEA		
ERYTHEMA		
EYE OEDEMA		
EYE SWELLING		
EYELID OEDEMA		
FACE OEDEMA		
FIRST USE SYNDROME		
FIXED ERUPTION		
FLUSHING		
GENERALISED ERYTHEMA		
HEADACHE		
HEART RATE INCREASED		
HOT FLUSH		

CA204-142
elotuzumab

Table 6:	MedDRA Terms	
HYPERHIDROSIS		
HYPERPYREXIA		
HYPERSENSITIVI	ΓY	
HYPERVENTILATION		
HYPOTENSION		
HYPOXIA		
INFLUENZA LIKE	ILLNESS	
INFUSION RELAT	ED REACTION	
KOUNIS SYNDRO	ME	
LARYNGEAL DYS	PNOEA	
LARYNGEAL OEI	EMA	
LARYNGOSPASM		
LARYNGOTRACH	EAL OEDEMA	
LIP OEDEMA		
LIP SWELLING		
MYOCARDIAL IN	FARCTION	
NAUSEA		
OEDEMA		
OEDEMA MOUTH		
OROPHARYNGEAL SPASM		
OROPHARYNGEA	L SWELLING	
OXYGEN SATURA	TION DECREASED	
PALPITATIONS		
PERIORBITAL OF	DEMA	
PHARYNGEAL OI	DEMA	
PRURITUS		
PRURITUS ALLERGIC		
PRURITUS GENERALISED		
PYREXIA		
RASH		
RASH ERYTHEM	TOUS	
RASH GENERALI	ED	
RASH MACULAR		
RASH MACULO-F	APULAR	

Table 6:	MedDRA Terms	
RASH MACULOVESIC	ULAR	
RASH PRURITIC		
RASH PUSTULAR		
RESPIRATORY ARREST		
RESPIRATORY DISTRESS		
RESPIRATORY FAILURE		
RESPIRATORY RATE INCREASED		
REVERSIBLE AIRWAYS OBSTRUCTION		
SENSATION OF FOREIGN BODY		
SHOCK		
SINUS TACHYCARDIA		
SKIN REACTION		
SKIN SWELLING		
SNEEZING		
STRIDOR		
SWELLING		
SWELLING FACE		
SWOLLEN TONGUE		
SYNCOPE		
TACHYCARDIA		
TACHYPNOEA		
THROAT IRRITATION		
THROAT TIGHTNESS		
TONGUE OEDEMA		
TRACHEAL OBSTRUC	TION	
TRACHEAL OEDEMA		
TYPE I HYPERSENSITIVITY		
TYPE II HYPERSENSITIVITY		
TYPE IV HYPERSENSITIVITY REACTION		
UPPER AIRWAY OBSTRUCTION		
URTICARIA		
URTICARIA PAPULAR		
VASCULITIC RASH		
VASCULITIS		

Table 6:MedDRA Terms

VOMITING

WHEEZING

APPENDIX 3 DEFINITIONS OF RESPONSE AND PROGRESSION CRITERIA (MODIFIED FROM IMWG)

Table 7:DEFINITIONS OF RESPONSE AND PROGRESSION CRITERIA
(MODIFIED FROM IMWG)

Response Subcategory	Response Criteria ^a
Stringent Complete Response (sCR)	CR, as defined below, plus the following:
	Normal FLC ratio ^b and absence of clonal cells ^c in bone marrow by immunohistochemistry or immunofluorescence.
Complete Response (CR)b	Negative immunofixation of serum and urine and disappearance of any soft tissue plasmacytomas, and < 5% plasma cells in bone marrow.
Very Good Partial Response (VGPR)	Serum and urine M-protein detectable by immunofixation but not on electrophoresis or $\geq 90\%$ reduction in serum M-protein level plus urine M-protein level < 100 mg per 24 hour.
Partial Response (PR)	\geq 50% reduction of serum M-protein and reduction in 24-hour urinary M-protein by \geq 90% or to < 200 mg per 24 hour. If serum and urine M-protein are unmeasurable, $a \geq$ 50% decrease in the difference between involved and uninvolved FLC levels is required in place of the M- protein criteria. In addition to the above criteria, if present at baseline, \geq 50% reduction in the size of soft tissue plasmacytomas is also required
Minor (Minimal) Response (MR)	25-49% reduction of serum M-protein and reduction in 24-hour urine M-protein by 50-89%, which still exceeds 200 mg per 24 hours. In addition, if present at baseline, 25-49% reduction in the size of soft tissuev plasmacytomas is also required. No increase in the size or number of lytic bone lesions (development of compression fracture does not exclude response).
Stable Disease (SD)	Not meeting criteria for CR, VGPR, PR, MR, or progression.
Progressive disease	Any of the following:
	• Increase of 25% from lowest response value in any one or more of the following:
	1. Serum M-component (absolute increase must be

Response Subcategory	Response Criteria ^a
	\geq 0.5 g/dL) ^d and/or
	2. Urine M-component (absolute increase must be \geq 200 mg per 24 h) and/or
	3. Only in patients without measurable serum and urine M-protein levels: the difference between involved and uninvolved FLC levels (absolute increase must be > 10 mg/dL)
	4. Bone marrow plasma cell percentage (absolute % must be $\geq 10\%$)
	• Definite development of new bone lesions or soft tissue plasmacytomas or definite increase in the size of existing bone lesions or soft tissue plasmacytomas
	• Development of hypercalcemia (corrected serum calcium > 11.5 mg/100 mL) that can be attributed solely to the plasma cell proliferative disorder

Table 7:DEFINITIONS OF RESPONSE AND PROGRESSION CRITERIA
(MODIFIED FROM IMWG)

^a All response categories require 2 consecutive assessments made at any time before the institution of any new therapy; all categories also require no known evidence of progressive or new bone lesions if radiographic studies were performed. Radiographic studies are not required to satisfy these response requirements. Bone marrow assessments need not be confirmed.

^b Note clarification to IMWG criteria for coding CR and VGPR in patients in whom the only measurable disease is by serum FLC levels: CR in such patients is defined as a normal FLC ratio of 0.26-1.65 in addition to CR criteria listed above. VGPR in such patients is defined as a > 90% decrease in the difference between involved and uninvolved FLC levels.

^c Presence or absence of clonal cells is based upon the κ/λ ratio. An abnormal κ/λ ratio by immunohistochemistry and/or immunofluorescence requires a minimum of 100 plasma cells for analysis. An abnormal ratio reflecting presence of an abnormal clone is κ/λ of > 4:1 or < 1:2.

^d For progressive disease, serum M-component increase of ≥ 1 g/dL is sufficient to define progression if starting M-component is ≥ 5 g/dL
